### Intervention

Intervention will be delivered only to the ORP group, at the baseline visit and at a 2 week booster session, to prepare the patient for weaning off of opioids.

During the intervention the interventionist will provide information regarding:

- Harms associated with opioid use (e.g., overdose and accidents)
- Tolerance & addiction risk factors
- Pain expectation following TKR surgery
- Non-narcotic pain management techniques
- Proper disposal of unused medication

Please refer to the intervention manual for more details on the intervention, such as:

- (a) Theoretical basis and overarching goals of the intervention
- (b) Treatment Schedule
- (c) Intervention Scripts
- (d) Patient Handouts
- (e) Interventionist Training
- (f) Intervention Fidelity

The intervention manual is located on onedrive in the CTSI TKR Opioid folder. The manual is specifically within the intervention folder.

# Follow-Ups & Data Abstraction

Following the baseline visit and surgery, we will engage with patients when they return to the Campbell Clinic for their Physical Therapy (PT) visits or over the phone to complete follow-up assessments. All participants will complete follow-up assessments with a Research Assistant (RA) blinded to treatment condition. Follow up assessments will occur at 4 weeks and 12 weeks following surgery.

Follow-ups consist of doing the measures for that visit and a data abstraction after the visit is complete.

Please see the measures section to review which measures are used during the follow-up visits.

**4-week abstraction:** This is a surgical note abstraction, meaning that we are looking for notes from the patient's physician within the Campbell Clinic health record system (SRS).

**12-week abstraction:** This will be a prescription based abstraction. Using the Campbell Clinic system and TN-CSMD will be required.

### **Campbell Clinic SRS**

The Campbell Clinic SRS is available to staff members who have been credentialed at Campbell Clinic. This process is overseen by the study coordinator and [name] (Campbell Clinic Research Nurse Coordinator). In order to access the SRS system, staff must VPN into the Campbell Clinic server using this link: https://citrixnew.campbellclinic.com/vpn/index.html (username/password are the Campbell Clinic credentials). Once logged in, staff needs to select the orange "SRS" icon the right end of the screen. This will start a download process. Double click the download, and it will load the health record system. You will need to sign in again with Campbell Clinic credentials.

If for some reason it doesn't work, you will need to make sure you have Citrix Receiver downloaded and/or call Campbell Clinic's IT line: [contact].

#### TN-CSMD

The TN-CSMD (Tennessee Controlled Substance Monitoring Database) is a database to monitor the dispensing of Schedule II, III, IV, & V controlled substances. We use this database during the 30-day data abstraction to see if the participant has been prescribed any opioids other than those prescribed by their Campbell Clinic surgeon.

#### **Registration**:

Accessing the TN-CSMD first requires a physician sponsor. We have used [name] of Campbell Clinic in the past.

#### 2. How do I register to access the CSMD database?

Go to www.tncsmd.com and click on the word "register" to begin the registration process. Completion of the registration process will require specific identifying elements. Once registration is complete and approved, you will receive an email with your username and instructions to create a password. Medical Examiner role is only for **State Medical Examiners**.

#### 6. What happens if I do not have a Tennessee driver's license?

You can still register at www.tncsmd.com, but you will need to obtain a Tennessee State ID. You will input the Tennessee State ID number into the Driver License field when registering. If you hold a Driver's License from another state you can register with the CSMD, but it may require manual validation by the CSMD Team.

#### **Using the CSMD:**

#### 18. How do I run a report to view the controlled substance history of a patient?

Once you are logged into the CSMD there is a step-by-step instruction available within the application by clicking the question mark ( ) in the dark blue bar on the right side. This will display text instructions to walk you through a patient request. Hover over the REQUEST tab on the top navigation bar. Then choose "New Request" and a page will appear that defaults to a PATIENT report. Fill in the patient's LAST NAME, FIRST NAME, and DOB (date of birth). Scroll down the page and locate the Date Range. It defaults to the past year, but you can change that by clicking on the checkmark in the box and entering the dates correctly (mm/dd/yyyy). You must choose the type of report output you want, either "PDF" or "XLS". If you would like to query other states to determine if your patient has data, mark the appropriate checkbox by the states, and then click SUBMIT at the very bottom of the page.

The system will show you an indicator (a green spinning wheel or taskbar depending on your browser) while it is searching the database. Multiple state data will be return if the user is authorized to view another state's data. Once the taskbar disappears, a screen will come up with the "Patient Rx History Report" link in the middle of the page. Click on that link and the file can be Opened or Saved. This link is only used if running data on the CSMD. If you run a multi-state report, please click the "**Display all Results**" button **instead** of the "Patient Rx History Report" hyperlink.

#### **COVID-19 Procedures**

#### **Baseline**

To safely adhere to COVID-19 procedures recruitment and baseline visits may be conducted remotely via telephone. Eligible participants will receive the consent form via DocuSign (or mail, if preferred and enough time is available) prior to meeting with research staff to allow time for review. Research staff will then conduct an informed consent process to ensure understanding from all participants. If consent was mailed, research staff must wait until signed consent is mailed back before continuing.

Once informed consent is complete, research staff will then assess participants and deliver the intervention, respectively. Participants in the ORP arm will also receive an e-mail with the recovery handout.

#### **Follow-Up Visits**

In addition to the baseline visit, all follow up visits may be conducted remotely via telephone by the research assistant (RA) or other staff member who is blinded to the participant's group placement.

### **Incentives**

Participants will receive a \$50 Amazon gift card for the Baseline visit, 4-week follow-up visit, and 12-week follow-up visit. Participants will receive a total of \$150 for completing all study visits.

Gift cards are ordered through the university's Amazon account where a template is to be downloaded from the site, filled out, and uploaded back onto the site to initiate the ordering process.

#### **Adverse Events**

An independent Data Safety Monitoring Board has not been established due to the very low probability of related serious adverse events. [name] will monitor AEs (adverse events) for this study.

If patients experience an adverse event during the study, we will conduct an assessment, complete an Adverse Event form, and follow the adverse event reporting system as required by our IRB and NIH regulations.

Adverse events (AEs) are defined as any unfavorable medical occurrence in a human subject, including any abnormal sign, symptom, or disease temporally associated with the subject's participation in the research, whether or not considered related to the subject's participation in the research.

Serious adverse events (SAEs) are any adverse event temporally associated with the subject's participation in research that meets any of the following criteria:

- Results in death
- Is life-threatening (places the subject at immediate risk of death from the event as it occurred)
- Requires inpatient hospitalization or prolongation of existing hospitalization
- Results in a persistent or significant disability/incapacity
- Results in a congenital anomaly
- Any other adverse event that, based upon appropriate medical judgment, may jeopardize the subject's health and may require medical or surgical intervention to prevent one of the other outcomes listed in this definition

All SAEs that are potentially related to the study are to be reported to the Project Coordinator ([name]) within one working day. The Project Coordinator will review and escalate to the PI and Study Physician (Drs. [name] and [name]) via email within 48 hours of initial documentation.

UTHSC's IRB operating procedures regarding AE's can be found here:

https://www.uthsc.edu/research/compliance/irb/researchers/documents/adverse-event-reporting.pdf

# **MEASURES**

# **SCHEDULING SCRIPTS**

Description of Data Collected	Measure/Document Name	Time to Compl ete	Baseline (pre-op)	4- week	12- week
General					
Eligibility Criteria	Eligibility TKR	1	Х		
Contact Information	Contact Info TKR	2	Х		
Demographics	Demographics	1	X		
Adverse Events	Adverse Event Reporting Tool	2		Х	х
Pain and Opioid Use					
History of Opioid Medication Use	History of Opioid Use	<1	Χ		
Pain catastrophizing	PCS	2	Х		
Opioid Medication Pill Count	Follow-Up Questionnaire	1		Х	Х
Opioid tolerance and craving	Follow-Up Questionnaire	<1		Х	Х
Current Opioid Misuse Measure	Current Opioid Misuse Measure	3		х	х
Quality and intensity of pain	SF-MPQ-2	4	Χ	Х	Χ
Short and long-term patient-relevant outcomes	KOOS JR	1	Х	Х	Х
Use of Non-Narcotic Pain Medication	Non-Narcotic Pain Medication	1	Х	х	Х
Engagement in Behavioral Pain Management Activities	Behavioral Pain Management Activities	1		х	Х
Pre/post knowledge of intervention content	Knowledge Test	1	Х	х	
Feedback and Satisfaction	Feedback	2			Х
Data Abstraction					
Prescriptions, surgery notes	Data Abstraction Tool	n/a		Х	Х
			14	16	17

### Scheduling Script for BV

What days/times are you usually available? We're usually available Monday-Friday from 8am-4:30pm. (Find a time before their surgery that works for both of you.) Great! I'll get you on the calendar for your first visit on DAY at TIME. (Let them know if you or someone else will be the one calling them.) You will need to

have access to your email/computer or smart phone for this visit so you can sign our electronic consent form. Do you have any questions or concerns about this visit? (Answer any questions they may have.) Thanks again for your interest in the TKR Study. We look forward to speaking with you again soon. Have a great day!

#### Recruitment Script for BSTR/FU (phone):

We've reached the end of your visit today, all I need to do now is get you scheduled for your next visit. (Look at participant's next visit window and try to find a day/time that works for them). Does DAY/TIME work? Great! I'll place you on the calendar for [VISIT TYPE] on DAY at TIME. (If you will not be the one doing the visit, let the participant know! For example: "My colleague, [NAME], will be the one calling you for this visit. Their number is [#].") Do you have any questions or concerns about your next visit?

#### Recruitment Script for BSTR/FU (in-person):

We've reached the end of your visit today, all I need to do now is get you scheduled for your next visit. (Look at participant's next visit window and try to find a PT visit that falls in that range). Does DAY/TIME work? Great! I'll place you on the calendar for [VISIT TYPE] on DAY at TIME. (If you will not be the one doing the visit, let the participant know! For example: "My colleague, [NAME], will be the one doing the visit with you.") Do you have any questions or concerns about your next visit?

# STUDY DOCUMENTATION

## **OneDrive & Filemaker**

#### **OneDrive**

All study forms (e.g. the consent form, study measures, the regulatory binder, this MOP, the randomization list, etc.) are kept on OneDrive. In order to access the TKR OneDrive folder, permission will need to be granted (i.e. the folder will need to be shared to each person's UT email).

#### Study Documentation (regulatory binder)

The regulatory binder is kept on OneDrive. This binder keeps track of our recruitment call log, enrollment, gift card payments, and appointment tracking.

#### **TKR Database**

The database is located on filemaker, a file hosting application on your UT computer/laptop. In order to access the database, the Research Manager has to request users to be added.

Once added to the TKR database, you will need to open filemaker and navigate to "File" at the top of your screen. Under "File" find "Hosts" and select "Show Hosts." It should pop up a new screen. On the new screen, hit the plus in the left hand corner (beside the search hosts bar) and type in: "filemaker.uthsc.edu" This should pull up several databases. (I suggest favoriting this host so you can easily access it in the future). You can either scroll or search for TKR to find the specific database: "CTSI TKR." (You can also add this specific database to your favorites.)

Now open the database by double clicking on the icon. You will log in with your UT net ID and password.

Opioid Reduction Program for Total Knee Replacement Patients Statistical Analysis Plan

NCT05414942

June 1, 2021

Data Analysis: The demographics and background variables across the two treatment groups will be compared to assess the integrity of the random assignment and check for expected balance between known covariates. Our primary analysis is an intent-to-treat analysis.

Aim 1: We will determine intentions to reduce opioid use at 4 weeks and differences in MMEs by group at 12 weeks based on general linear and mixed models that account for the repeated measures and available covariate information (gender, race, age, socioeconomic status, etc., as well as relating to amount of opioid prescribed and experienced pain levels). The main independent variable in each analysis is treatment assignment (marginal p-value of 0.05 used as cut off to declare significance). We will also test mediation and moderation using covariates listed in the measures. Especially, we will conduct a descriptive heterogeneity of treatment effect analysis (HTE)² with respect to sex/gender and race. Our study is not powered to detect interaction effects and the descriptive nature of this HTE suggests that we will not adjust for multiplicity in testing.²

Aim 2: We will conduct a linear regression to examine the predictive utility of cumulative MMEs on functional recovery total score as an outcome at each follow up visit. Possible confounders like pain (allowing for more activities as well as reduction of opioids) will be especially studied.

References

- 1. VanderWeele TJ. Explanation in Causal Inference Methods for Mediation and Interaction. New York: Oxford University Press; 2015.

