# **PROJECT OVERVIEW**

### **Purpose**

The purpose of this work is to examine the efficacy of a brief intervention to reduce opioid use following total knee replacement.

We will conduct a randomized clinical trial to test our newly adapted Opioid Reduction Program ORP (vs. Treatment As Usual; TAU) for a population of patients presenting for Total Knee Replacement (TKR) surgery (N=100). Our intervention will include a discussion of the risks of opioid use, pain management through nonnarcotic medication and mindfulness techniques, and opioid weaning strategies that will assist patients with reductions in opioid use, even for those with chronic pain. We will assess outcomes using opioid refill requests, prescription drug monitoring, and pill counts of opioid medication at 4 weeks (short term follow up) and 12 weeks (long term follow up) following TKR surgery.

**Aim 1:** Examine the efficacy of our ORP vs. TAU control in reducing opioid use among TKR surgery patients. Opioid use following TKR surgery will be assessed via daily diaries, pill counts, medical chart review of prescription refills, and prescription drug monitoring for opioid refills from other physicians.

**Hypothesis 1**: We hypothesize that at 4 weeks, a higher percentage of those in the OPR group will express an intent to reduce future opioid medication use as compared with those in TAU.

**Hypothesis 2**: We hypothesize that those in the ORP will have lower cumulative exposure to opioid medication (i.e., morphine milligram equivalents [MMEs] at 12 weeks) than those in TAU.

Aim 2: Examine the relation between opioid use and TKR functional recovery following surgery.

**Hypothesis 3**: We predict that those who reduce their opioid use (as evidenced by fewer MMEs) will engage more in activities that will increase range of motion and functional knee use (e.g.,physical therapy and athome exercises), thereby increasing the speed of recovery.

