# **Eligibility**

#### **Inclusion Criteria**

To be eligible to participate, participants must meet the following requirements:

- Presenting for a pre-operatory appointment at Campbell Clinic for TKR surgery that will result in the prescribing of opioid medication
- 18 years of age or older
- Have access to a telephone
- Be able to understand consent procedures

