#### **Outcome Measures**

Outcomes Aim 1: We will assess regular opioid use prior to and following surgery, using a daily diary of opioid medication use, opioid medication pill counts, information transcribed from the medical file (medication prescribed and prescription refill requests), and prescription drug monitoring data.

Outcomes Aim 2: We will assess functional recovery using the Knee Injury and Osteoarthritis Outcome Score. In addition to our main outcomes, we will assess potential confounders and moderators of treatment, including history of and current chronic pain, pain catastrophizing, opioid tolerance and craving, adverse events, knowledge about opioid risks prior to/following intervention, and transcribed surgical specifics from the medical file (analgesia, complications).

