# Randomization

Randomization happens during the Baseline Visit, after all the assessments are complete. *Please note that randomization and treatment (ORP) must occur during the same visit*. The randomization scheme is as follows:

CTSI-TKR is a prospective randomized clinical trial with two treatment arms (n = 50 each for a total of 100 participants): Opioid Reduction Program (ORP) and Treatment As Usual (TAU). Participants are individually

assigned to a study arm by stratified variable-block randomization (randomly chosen block-lengths of 4 or 6 and separate sequences in each of the two strata defined by sex/gender).

The randomization scheme was determined by the statistician and can be found under the "Study Management" folder. Within the randomization log, simply locate the appropriate tab (according to your participant's gender) and find the next blank, which will tell you if that person is in ORP group (intervention) or TAU group (control). Make sure to fill out the study ID number, date of BV, and transfer the allocID to the participant's database profile.

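### The Aim 1 models adjust for opioid prescribed and pain without limiting either to pre-randomisation values, so the 12-week MME coefficient may not be the total intent-to-treat effect

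*SAP*

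**What the plan says.** The SAP's Data Analysis section states that the primary analysis is intent-to-treat. For Aim 1 it names general linear and mixed models that use demographic covariates and further information described "as well as relating to amount of opioid prescribed and experienced pain levels". Treatment assignment in these models is tested at 0.05. There is no unadjusted or baseline-only Aim 1 model, and no time point for either covariate. Mediation is listed separately: "We will also test mediation and moderation using covariates listed in the measures".

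The protocol fixes the order of events. In its Randomization section, "Randomization happens during the Baseline Visit, after all the assessments are complete", and that visit is before surgery. In its Intervention section, "Intervention will be delivered only to the ORP group, at the baseline visit and at a 2 week booster session".

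Prescribing data are also outcome data. The Aim 1 text under Purpose lists "medical chart review of prescription refills, and prescription drug monitoring for opioid refills from other physicians", and Outcome Measures lists "information transcribed from the medical file (medication prescribed and prescription refill requests), and prescription drug monitoring data".

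**The concern.** Hypothesis 2 is about cumulative morphine milligram equivalents (MME) by arm at 12 weeks, which is a total effect of assignment. ORP aims to make patients need and request less opioid and to manage pain in other ways. Refills and post-operative pain are therefore plausible consequences of treatment. Conditioning on them removes the part of the effect that runs through them. If something unmeasured, such as opioid need, drives both the covariate and MME, conditioning also breaks the comparability that randomisation created.

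The intent-to-treat label does not settle this, because it governs who is analysed in which arm and not which covariates may enter. As written, the main result could be a total or a partial effect, and the choice could be made after the data are seen.

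**Working it through.** **Step 1. What each covariate could mean.**

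| Covariate | Reading | Support in the documents | Consequence |
|---|---|---|---|
| Amount prescribed | Before randomisation | Outcome Measures: "We will assess regular opioid use prior to and following surgery"; the state monitoring report defaults to the past year | Valid covariate |
| | Initial surgical prescription | Inclusion Criteria: "Presenting for a pre-operatory appointment at Campbell Clinic for TKR surgery that will result in the prescribing of opioid medication" | After randomisation; no bias if ORP does not change it |
| | Prescriptions and refills to 12 weeks | Measures table schedules abstraction at 4 and 12 weeks only; the 12-week abstraction is prescription-based | Conditions on a possible effect of ORP and on outcome data |
| Pain | Baseline | Chronic pain listed among confounders and moderators; baseline SF-MPQ-2 | Valid covariate |
| | Post-operative | SF-MPQ-2 at 4 and 12 weeks; early post-surgical pain asked at follow-up | Conditions on a possible effect of ORP |

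**Step 2. Loss of the mediated part.** The plan states no power, effect size or SD, so there is no figure to reproduce. The documents give 50 per arm and the 0.05 cut-off (taken as two-sided). Everything else here is assumed: total effect -0.60 SD and within-arm outcome variance 1. Unadjusted, the standard error is √(2/50) = 0.20 and power is about 84%.

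Model: Y = dT + 0.3X + 0.4I + 0.5R + e, where X is pre-randomisation prescribing, I the initial prescription and R = aT + N(0,1) the refills. X and I are unit-variance and unaffected by T, and d is set so that the total effect is -0.60. If refills carry share s of the effect, a = -0.60s/0.5 = -1.2s.

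- Adjust for X or I: the coefficient stays at -0.60, with power 87–88% (X) or 89–90% (I).
- Adjust for I and R as one summed amount: the within-arm slope is (0.4 + 0.5)/2 = 0.45, so the coefficient is -0.60 - 0.45a = -0.60 + 0.54s.
- Adjust for I and R separately: the coefficient is -0.60 - 0.5a = -0.60(1 - s). Residual variance is 1 - 0.16 - 0.25 = 0.59 and SE² = (2/50)(0.59)(1 + a²/4).

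| Share s | Summed: coefficient | Power | Separate: coefficient | Power |
|---|---|---|---|---|
| 0% | -0.60 | 97% | -0.60 | 97% |
| 20% | -0.49 | 88% | -0.48 | 87% |
| 40% | -0.38 | 68% | -0.36 | 62% |
| 70% | -0.22 | 28% | -0.18 | 19% |
| 90% | -0.11 | 10% | -0.06 | 6% |

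Coefficients come from the formulas. Power is from 8,000 simulated trials (summed) and the noncentral t distribution (separate).

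With post-operative prescriptions and pain both in the model (slopes 0.7 and 0.3), the coefficients at the same total shares are -0.60, -0.48, -0.36, -0.18 and -0.06, with power 99, 95, 77, 26 and 7%. Below a share of about 35%, adjustment raises power while still changing what is estimated.

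**Step 3. Direction under a shared cause.** Let pain Q = aT + lU + e and Y = tT + lU + e, with U unmeasured and within-arm variances 1. The within-arm slope of Y on Q is l², so the adjusted coefficient is t - al².

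- t = 0, l = 0.3, a = -0.2: 0 + 0.2 × 0.09 = +0.02 (5.5% false positives).
- t = 0, l = 0.6, a = -0.5: 0 + 0.5 × 0.36 = +0.18 (14.7%). This is the extreme case.
- t = 0, l = 0.6, a = +0.3: 0 - 0.3 × 0.36 = -0.11 (8.3%).
- t = -0.60, l = 0.6: -0.60 + 0.108 = -0.49 if ORP lowers pain by 0.3, and -0.60 - 0.108 = -0.71 if it raises it by 0.3.

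**Step 4. The 4-week intention outcome.** With an assumed 50% v 70% and no shared cause, adjusting for post-operative pain that carries 40% of the effect turns 20 points into 12. Power falls from about 54% to 27%.

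**The case against.** The SAP does not commit to post-randomisation adjustment. The covariate list opens with background characteristics, the preceding paragraph speaks of known covariates in the context of baseline balance, and the protocol counts chronic pain among confounders and moderators. Two of the three readings of amount prescribed cause no bias, the second provided ORP leaves the initial prescription unchanged. On this view the defect is only an unstated time point. That is a fair account of the ambiguity but does not remove it: the only scheduled prescription abstraction comes after randomisation, so the plan as written leads most naturally to the problematic reading of that covariate. For pain the text is open both ways.

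Three narrower points stand. Every slope, share and loading above is assumed, and high mediated shares have no anchor in the documents. If MME is itself built from prescription records, refills are a component of the outcome, which the Step 2 model does not represent. Last, the monitoring report's one-year default is a general instruction for using the database and not a trial data item, and the content of the opioid history form is not shown; whether pre-randomisation amounts will be available is therefore uncertain.

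It is also true that barring the initial surgical prescription is stricter than necessary if ORP cannot influence it. That is a conservative choice with a precision cost.

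**Conclusion.** The concern holds. The SAP does not fix whether its Aim 1 treatment coefficient is a total or a partial effect, because two of its covariates can be read as variables measured after randomisation, and one of these also supplies outcome data. The bias is conditional. It is absent if only pre-randomisation values are used, or if the prescription used is an initial one that ORP does not change. Otherwise the loss grows with the share of the effect that passes through the covariates. Under the stated assumptions, -0.60 SD becomes between -0.49 and -0.11 SD for refill-mediated shares of 20% to 90% (summed covariate). A shared cause can move the estimate either way, negligibly at loadings of 0.3 and by up to 0.18 SD in the most extreme case examined. These figures illustrate a range and do not predict this trial's result. The point should be settled before analysis, because it determines what the main Aim 1 result means.

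**What to change.** Replace the covariate wording for Aim 1 with text to this effect:

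> The primary Aim 1 models include treatment arm, sex/gender (the stratification factor) and covariates measured before randomisation only, including baseline SF-MPQ-2 pain and baseline opioid history. Amount of opioid prescribed, where used, is limited to prescriptions dated before randomisation. Opioids prescribed after randomisation and post-operative pain do not enter the primary models; they are used only in the mediation analysis or in a labelled sensitivity analysis.

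This needs no new data collection: baseline SF-MPQ-2 and the opioid history form are already scheduled. Pre-randomisation prescriptions are optional and depend on whether the monitoring report can supply them.

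The cost is some precision if ORP affects neither prescribing nor pain. In the assumed models, power would then be 84% with no covariate, against 90% with the initial prescription or 99% with both post-operative covariates. Baseline covariates that explain 10, 20 or 30% of within-arm MME variance bring it to 88, 91 or 94%, with the estimate still at -0.60 SD.

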### **Cascade of Events**

#### **Baseline**

Contact potential participants prior to surgery to provide information about participation

- Screening for eligibility/exclusionary criteria
- Informed Consent
- Baseline assessments
  - Contact Information
  - Demographics
  - History of opioid use
  - Non-narcotic pain medication use
  - Knowledge pre-test
  - Quality and intensity of pain (SF-MPQ-2)
  - Short and long-term patient-relevant outcomes (KOOS JR)
  - Pain catastrophizing
- Randomization to Opioid Reduction Program (ORP) vs. Treatment As Usual (TAU; no intervention)
- ORP only:
  - For the experimental group:
    - ORP discussion including the following topics: risks of opioid use, tolerance and addiction, consequences of using opioids with alcohol or other sedatives, appropriate use of opioid medication, use of acetaminophen/ibuprofen in place of opioid, and appropriate disposal of opioid
- Provide incentive (Amazon gift card sent directly to participant's email, or ordered and printed for participant to take) for participation in visit 1
- Set appointment date/time for booster (ORP arm) or 4-week follow-up (TAU arm)

ORP only: Booster Session (In-person at Campbell Clinic or over-the-phone, 2wks post op)

Delivery of ORP booster intervention 2-weeks after surgery

4-Week Follow-Up (In-person at Campbell Clinic or over-the-phone)

- Assessment of: Opioid medication pill count and regimen (when taken, number of pills taken per
  dose), pain in the days following surgery, current pain, knowledge post-test, use of other pain
  management, and self-report of opioid takeback for disposal, opioid tolerance and craving, adverse
  events, opioid daily diary.
- Medical record abstraction including surgery specifics (analgesia, complications), functional recovery, and medication refills.
- Provide incentive for participation in follow-up (Amazon gift card sent directly to participant's email, or ordered and printed to mail to participant)

12-Week Follow-Up (In-person at Campbell Clinic or over-the-phone)

- Assessment of: Opioid medication pill count and regimen (when taken, number of pills taken per
  dose), pain in the days following surgery, current pain, knowledge post-test, use of other pain
  management, and self-report of opioid takeback for disposal, opioid tolerance and craving, adverse
  events, opioid daily diary.
- Medical record abstraction including medication refills and functional recovery.

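### The Aim 2 regression of follow-up function on cumulative MME does not commit to baseline KOOS JR, although the trial already collects it

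*SAP*

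**What the plan says.** SAP, Data Analysis, Aim 2 specifies a "linear regression to examine the predictive utility of cumulative MMEs on functional recovery total score as an outcome at each follow up visit". On confounding it adds one sentence: "Possible confounders like pain (allowing for more activities as well as reduction of opioids) will be especially studied". It gives no covariate list, does not mention baseline function or change from baseline, does not say whether the pain is measured at baseline or follow-up, and states no significance cut-off for this aim.

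The protocol (Purpose) words Aim 2 as "Examine the relation between opioid use and TKR functional recovery following surgery". Hypothesis 3 goes further: lower opioid use is predicted to lead to more activity, "thereby increasing the speed of recovery".

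KOOS JR and SF-MPQ-2 are listed among the baseline assessments (Cascade of Events, Baseline). The Measures table schedules both at baseline, 4 weeks and 12 weeks.

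Two other places come close to a covariate list:

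- Protocol, Outcome Measures, Aim 2 paragraph: "we will assess potential confounders and moderators of treatment, including history of and current chronic pain". It goes on to catastrophizing, tolerance and craving, adverse events, knowledge and surgical details. Baseline function is not named.
- SAP, Aim 1: "We will also test mediation and moderation using covariates listed in the measures". The Measures table includes baseline KOOS JR, but this sentence belongs to Aim 1 and concerns mediation and moderation.

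**The concern.** Patients are compared here by the opioid they took, so randomisation does not protect the comparison. If patients with worse function before surgery take more opioid and also score worse afterwards, a negative slope appears even when opioid use has no effect on recovery.

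One part of the concern needs no numerical assumption. Hypothesis 3 is about recovery, but the model's outcome is a follow-up level. A patient who starts low and ends low may have recovered as much as one who starts and ends high, and without the starting value the model cannot tell them apart.

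At stake is the reading of Hypothesis 3. An open covariate set also leaves the choice of adjustment until after the data are seen.

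**Working it through.** **Plan's own figure.** None to reproduce: the documents give no expected slope, SD, correlation or power for Aim 2. From the documents come n = 100 (protocol, Randomization) and the form of the model. Everything else is assumed.

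**Assumptions.** The functional score is KOOS JR, coded so that higher is better. All variables are standardised, and the true MME effect is 0. B is baseline function, P baseline pain, M cumulative MME and F follow-up function. In absolute value, rM = corr(B, M), rF = corr(B, F) and rP = corr(B, P). Main range: rM 0.2–0.4, rF 0.3–0.5, rP 0.5–0.7. The slope is tested at two-sided 0.05, a rule Aim 2 does not state, and only negative slopes are counted, so nominal is 2.5%.

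**Expected slope, no covariates:** −rM·rF.
- (0.2, 0.3): −0.06
- (0.4, 0.5): −0.20

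**Expected slope after adjusting for baseline pain**, under three mechanisms:
- *Pain alone drives MME:* 0.
- *Half through function, half through pain:* −(rM/2)·rF·(1−rP²)/(1−c²), with c = rM·rP/2 + rM/(2rP). At (0.4, 0.5, 0.5), c = 0.1 + 0.4 = 0.5, so −0.2 × 0.5 × 0.75/0.75 = −0.10. At (0.2, 0.3, 0.7), c = 0.07 + 0.143 = 0.213, so −0.1 × 0.3 × 0.51/0.955 = −0.016.
- *Pain is only a proxy for function:* −rM·rF·(1−rP²)/(1−rM²·rP²). At (0.4, 0.5, 0.5), −0.20 × 0.75/0.96 = −0.156. At (0.2, 0.3, 0.7), −0.06 × 0.51/0.9804 = −0.031.

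**False negative-slope rate (%)**, n = 100, 20,000 simulated trials per cell. Pairs are rP = 0.5 / 0.7.

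| rM, rF | No covariates | Pain-adjusted: proxy | Pain-adjusted: half | Pain-adjusted: pain alone |
|---|---|---|---|---|
| 0.1, 0.3 | 4.8 | 4.2 / 3.5 | 3.0 / 3.2 | 2.5 / 2.6 |
| 0.2, 0.3 | 8.5 | 6.6 / 4.7 | 4.1 / 3.8 | 2.5 / 2.6 |
| 0.2, 0.5 | 17.0 | 11.9 / 7.9 | 5.6 / 4.4 | 2.4 / 2.4 |
| 0.3, 0.4 | 21.5 | 14.6 / 9.5 | 7.1 / 5.5 | 2.4 / 2.5 |
| 0.4, 0.5 | 51.4 | 34.5 / 20.2 | 13.5 / 8.4 | 2.6 / 2.4 |

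With rM = 0 and rF = 0.4 the rate is 2.3–2.6% throughout. With baseline KOOS JR and pain together it is 2.3–2.7% for rM ≥ 0.2. That is by construction, since no other confounder was simulated.

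**Why pain as well as KOOS JR.** If pain drives MME and also affects follow-up function directly, KOOS JR alone leaves 9–54%; the two together give 2.4–2.6%.

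**Why arm as well.** ORP aims to lower MME and also teaches non-narcotic pain management and mindfulness, which could affect function by another route. With assumed arm effects of about 0.5 SD on MME and 0.3–0.5 SD on function (half mechanism; rM 0.2, rF 0.4, rP 0.6), KOOS JR plus pain leaves about 5.5–9.6%. Adding arm gives 2.4–2.6%.

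**Precision.** The cut in residual variance from baseline KOOS JR beyond pain is 1 − (1−rF²)/(1−rF²·rP²).
- rF 0.3, rP 0.7: 1 − 0.91/0.9559 = 4.8%
- rF 0.5, rP 0.5: 1 − 0.75/0.9375 = 20%

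**The case against.** The strongest reply is that the SAP has already named the path that matters. Its only stated mechanism is pain acting on both activity and opioid use. If pain alone drives MME and baseline pain is adjusted, the spurious slope is 0 and the false rate is nominal. The larger pain-adjusted figures need function to drive MME beyond pain, which no passage says. This stands, with one limit: the SAP does not say that the pain it will study is baseline pain.

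The aim is also worded as a relation and as predictive utility. For that reading the unadjusted slope is a genuine association, and only the causal wording of Hypothesis 3 is exposed. This stands too.

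History of opioid use and catastrophizing are collected at baseline as well and are plausible drivers of MME, so singling out KOOS JR may look like preference. In part it is, and nothing here argues against adding them. KOOS JR comes first because it is the starting value of the outcome itself.

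A reader might infer that the SAP leaves baseline function out of the model, or intends no adjustment. The documents do not support that: the confounder wording is open, and the protocol's own list is introduced as illustrative. The gap is a missing commitment.

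**Conclusion.** The concern holds in a limited form. The Aim 2 models should commit to the baseline value of their own outcome, and at present they do not. If baseline function influences MME beyond pain, part of a negative slope could reflect starting level.

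The size cannot be found from the documents. Over the main assumed range the pain-adjusted false rate is 2.4–2.6% if pain alone drives MME, 3.8–13.5% if pain and function share the role, and 4.7–34.5% if pain is only a proxy. At correlations of 0.1 and 0.3 it is 2.5–4.2%, and if baseline function is unrelated to MME there is no inflation.

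A reader might take the 8.5–51.4% for the model without covariates as the error rate of the planned analysis. It is not: the SAP intends to examine confounders, every correlation is assumed, and Aim 2 sets no cut-off. Nor does the point reach the ORP versus TAU comparison, because no treatment-effect estimate depends on this regression.

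**What to change.** Amend SAP Aim 2 as follows:

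- Include baseline KOOS JR, baseline SF-MPQ-2 pain and treatment arm as covariates in both the 4-week and the 12-week model.
- Report the MME slope with and without follow-up pain as a sensitivity analysis, since opioid use may itself change that pain.
- Interpret Hypothesis 3 as an association, because these covariates do not remove all confounding.

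The gain is less confounding by starting level and, under the assumed correlations, about 5–20% less residual variance. The cost is SAP wording and three degrees of freedom: with intercept and MME slope, 100 − 5 = 95 remain if all 100 participants are analysed. No new data are needed.

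Separately, the protocol places the TN-CSMD query at the 12-week abstraction in Follow-Ups & Data Abstraction but at a 30-day abstraction in the TN-CSMD section. These should be reconciled because they bear on how MME is ascertained, but they lend no support to this point.
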